#### **Inpatient Period**

The inpatient period refers to the period from the date of first study intervention dispensation of SZC until the date of randomisation at discharge (exclusive) or until 21 days after the first dose of SZC for participants who have not been randomised.

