6.1 Screening and Inpatient Phase

Participants with HK (see inclusion criterion #4) and not on SZC or patiromer before this current ED visit/hospital admission (initiation of SZC or patiromer during ED visit/hospitalisation preceding enrolment is allowed), will start SZC, as per local label, during the inpatient phase. Initiation of SZC treatment will be based on local measurement of K⁺, obtained within 24 hours prior to first dose of on-study SZC:

- Correction treatment: 10 g, TID for up to 72 hours. Typically, NK is achieved within 24 to 48 hours. If participants are still hyperkalaemic after 48 hours of treatment, the same regimen can be continued for an additional 24 hours. If NK is not achieved after 72 hours of treatment, other treatment approaches should be considered, and the participant discontinued from the study due to lack of SZC effect. Participants who received any HK treatment during current ED visit/hospitalisation preceding enrolment and are NK at baseline can directly start the maintenance dose of SZC (see hereafter).
- Maintenance treatment (once NK [K^+ between 3.5 and 5.0 mmol/L, inclusive] is reached): 5 g, QD. Dose will be adjusted based on K^+ (see [Table 4](#)). The recommended maintenance dose range is from 5 g every other day to 10 g daily.

Participants with NK and who have been started on a maintenance dose for SZC (per local label) at the time of discharge will be randomised at discharge to either Arm A (SZC per local label) or Arm B (SoC, as per local practice) and enter the outpatient phase.

The following participants will not be eligible for randomisation:

- Participant intended to be discharged on a K-binder as per the site routine medical practice (discontinued from the study)
- Participant with an in-hospital phase exceeding 21 days (including screening), except when study medical monitor's approval was sought for longer duration of hospital stays for specific participants
- Participants with $K^+ > 5.0$ mmol/L at discharge; these participants will be discontinued from the study treatment and followed up as per protocol
- Participants with $K^+ < 3.5$ mmol/L at discharge; these participants will be discontinued from study treatment and will be followed per protocol.

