**Table 1 Definition of visit windows during the inpatient period**

Visit	Target Day of Visit	Visit Window
Visit 1	Date of Informed Consent	NA a
Visit 2	Date of first dose of SZC	NA

a For potassium measurements only, the visit windowing will allow any potassium measurement recorded prior to the date of informed consent

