**Table 3: Definition of visit windows during the outpatient period for all other assessments**

Visit	Study Day a	Target Day of Visit b	Protocol Visit Window b	Analysis Visit Window b
Visit 3	2 to 21	Date of randomisation	NA	NA
Visit 4	9 to 28	7	6 to 8	2 to 45
Visit 7	92 to 111	90	84 to 96	46 to 135
Visit 10	182 to 201	180	174 to 186	136 to 186

a Relative to the date of first study intervention dispensation of SZC during the inpatient phase

b Relative to the date of randomisation

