##### **4.6.3.2 Presentations**

Laboratory data (clinical chemistry and haematology) will be summarised and listed. Laboratory data outside the reference ranges will be indicated in the listings. If a participant has multiple results for a particular test at a particular time point, the rules of section 3.3.2 will be followed. System international (SI) units will be reported for all analytes.

Laboratory data absolute and change from baseline values for continuous chemistry and haematology parameters will be summarised at each scheduled assessment time. Separate tables will be provided for the SSO, restricted to visits during the inpatient period and presented overall and for the SSR, which will include all visits and be presented by treatment received during the outpatient period.

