##### **4.6.4.2 Presentations**

Shift tables will be presented where shift from baseline to the maximum value will be summarised. These will be provided separately for the SSO, which will be limited to visits during the inpatient period, and the SSR, which will summarize the worst overall value across all visits.

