##### **4.6.6.2 Presentations**

Vital sign values will be summarised and listed. Vital sign data absolute and change from baseline will be summarised at each scheduled timepoint. The continuous vital sign parameters will be summarised with descriptive statistics. If a participant has multiple results for a particular test at a particular time point, the result selected by the rules in section 3.3.2 will be used for the summary. These will be provided for the SSO, limited to visits during the inpatient period and presented overall, and the SSR, which will include all visits with scheduled vital sign assessment and be presented by treatment received during the outpatient period.

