#### **4.6.7.2 Presentations**

ECG data will be summarised and listed. Absolute and change from baseline in ECG parameters will be summarised at each scheduled timepoint. The continuous ECG parameters will be summarised with descriptive statistics. If a participant has multiple results for a particular test at a particular time point, the result selected per rules in section 3.3.2 will be used for the summary. These will be provided for the SSO, limited to visits during the inpatient period and presented overall, and the SSR, which will include all visits with ECG assessments and be presented by treatment received during outpatient period.

All summaries of ECG data will exclude observations from site 7001 where a serious breach in the collection of ECG results was identified.

The number and percentage of participants with QTcF results exceeding ICH boundaries ( $>450$ ms,  $>480$ ms,  $>500$ ms), with increases from baseline  $>30$ ms,  $>60$ ms,  $>90$ ms, decreases from baseline  $>30$ ms,  $>60$ ms,  $>90$ ms and for each combination of post-baseline values ( $>450$ ms,  $>480$ ms,  $>500$ ms) and increases ( $>30$ ms,  $>60$ ms,  $>90$ ms) will be presented for the SSO, limited to visits during the inpatient period and presented overall, and the SSR which will include all visits with scheduled ECG assessment and be presented by treatment received during the outpatient period. Participants are included based on maximum QTcF value and are counted in all cumulative categories (e.g., a participant with a QTcF value of 510ms would be included in 450ms, 480ms and 500ms rows).

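### For randomised participants, the in-hospital (SSO) laboratory, urinalysis, vital-sign and ECG tables hold no scheduled record after the first study dose, because the inpatient period stops before Visit 3

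*SAP*

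**What the plan says.** SAP section 3.3.1.2 sets the inpatient period for randomised participants "from the date of first study intervention dispensation of SZC until the date of randomisation at discharge (exclusive"). For those not randomised it runs to 21 days after the first dose. The outpatient period begins on the randomisation date. Protocol Table 8 (section 9.3) excludes the randomisation date in the same way.

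SAP Table 1 ("Definition of visit windows during the inpatient period") lists only Visits 1 and 2. Table 3 ("Definition of visit windows during the outpatient period for all other assessments") lists Visit 3, with the date of randomisation as its target, and Table 2 does the same for admissions and ED visits.

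The in-hospital safety tables depend on that period:
- Blood laboratory, SAP 4.6.3.2: "Separate tables will be provided for the SSO, restricted to visits during the inpatient period and presented overall".
- Urinalysis shift, SAP 4.6.4.2: "SSO, which will be limited to visits during the inpatient period".
- Vital signs, SAP 4.6.6.2: "limited to visits during the inpatient period and presented overall".
- ECG, SAP 4.6.7.2: "These will be provided for the SSO, limited to visits during the inpatient period and presented overall".

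The Protocol's Schedule of Activities places Visit 3 in the in-hospital phase, and section 1.1 puts randomisation on that day. Section 6.1 bars randomisation when discharge potassium is above 5.0 or below 3.5 mmol/L. Of the low group it says that "these participants will be discontinued from study treatment and will be followed per protocol".

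**The concern.** The SSO covers everyone who received study SZC in hospital, including the correction phase. At 10 g three times daily (30 g/day), that is a higher daily exposure than the outpatient range, which tops out at 10 g daily (Protocol 6.1 and 6.2). Protocol 2.3.1 names hypokalaemia as a major risk. Protocol 9.4.4 asks for safety analyses on both the SSO and the SSR, with laboratory shifts to the worst value within each part of the study.

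If the period closes the day before the discharge assessment, the tables meant to describe safety on SZC in hospital show baseline values and little else for most participants. What on-treatment evidence remains would come from those who did not reach randomisation. A reader of the study report could take such a table as a description of the whole treated in-hospital population.

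**Working it through.** No test or power figure is involved. The check sets the visit schedule against the period rule and then sizes the two groups.

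**Step 1. Visit 3 against the period.** Visit 3 is the randomisation date. The period excludes that date, so Visit 3 is outside it for every randomised participant.

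**Step 2. What remains inside the period for a randomised participant.** Schedule from Protocol Table 1; period from SAP 3.3.1.2; baseline from SAP 3.3.1.1 (last value before the first study dose).

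| Domain | Scheduled in hospital | Inside the inpatient period | Scheduled visit after first study dose and inside |
|---|---|---|---|
| Central safety laboratory, dipstick | Visits 2, 3 | Visit 2 (baseline) | none |
| Vital signs | Visits 1, 2, 3 | Visit 2 (baseline) | none |
| ECG | Visits 1, 3 | normally none; Visit 1 usually precedes the period start | none |
| Local potassium | Visits 1, 3, and at least daily during correction | the daily values, by date | the daily values, but with no window |

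The last row matters because footnote i of the Schedule of Activities requires at least daily potassium during correction. SAP Table 1 gives no window between Visits 2 and 3, and SAP 3.3.3 sends unscheduled values back to those same window rules.

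**Step 3. Participants not randomised.** Their discharge or early-discontinuation assessment is inside the period if made within 21 days of the first dose. By-visit tables still have no slot for it. Table 1 stops at Visit 2, Visit 3 in Tables 2 and 3 is anchored to a randomisation that did not occur, and Table 4 covers only the follow-up visit. The urinalysis shift to maximum and the maximum-QTcF categories need no visit slot, so these participants' values can enter there.

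**Step 4. Size.** Inputs from Protocol 1.1: 104 evaluable, 20% loss before and 20% loss after randomisation.
- Randomised: 104 / 0.8 = 130, as the Protocol states.
- Enrolled: 130 / 0.8 = 162.5, rounded up to 163, as stated.
- Not randomised: 163 − 130 = 33, or 33 / 163 = 20.2%. This is an upper bound for the SSO, since some may never be dosed.
- With no scheduled post-dose SSO record in the four domains: 130 / 163 = 79.8% of those enrolled.

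**The case against.** The strongest reply is that little is lost. SSR laboratory, vital-sign and ECG tables include all visits, and SSR urinalysis takes the worst value across all visits, so randomised participants' Visit 3 results are tabulated there. These laboratory, vital-sign and ECG data are also listed. Confirmed potassium below 3.5 mmol/L must be reported as an adverse event (Protocol 8.3.5), and SSO adverse-event tables cover the inpatient period. The SAP also follows Protocol Table 8 faithfully. All of this stands, and it limits the point to descriptive tables. It does not repair them: the SSR splits the in-hospital result by an arm assigned afterwards and omits participants who were never randomised.

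A reader might also infer more than the documents support:
- That the SSO tables contain no on-SZC data at all. Non-randomised participants stay in the period to Day 21, and their values can reach the maximum-based tables. Some participants may also already be on SZC at baseline, because starting it earlier in the same hospital stay is allowed.
- That the SSO QTcF counts come only from the screening ECG. By date, that ECG normally falls before the period opens.
- That participants with discharge potassium below 3.5 mmol/L appear in no laboratory table. The period rule keeps them in. What is missing is a specified by-visit slot, and SAP 3.3.2 does not say that an unlisted visit is dropped.
- That the 4.1% hypokalaemia rate in Protocol Table 2 gives the number of records affected. It is a rate from earlier trials, and the documents give no rate at discharge.

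**Conclusion.** The point holds for randomised participants. Followed as written, the SSO laboratory, urinalysis, vital-sign and ECG tables have no scheduled post-first-dose record for about 130 of about 163 planned participants. On-treatment entries in these domains could come essentially only from the non-randomised group, at most about 33 and selected partly for abnormal potassium. The daily correction-phase potassium has no window.

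This rests on the planned numbers and on applying the period dates and visit tables literally. Unscheduled assessments before randomisation could add a few values, but the plan does not schedule or window them. No efficacy analysis, error rate or sample size is affected, and the adverse-event tables are sound. The SAP should still be corrected before database lock, since the in-hospital tables would otherwise be nearly empty of on-treatment data or drawn from a selected group.

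**What to change.** In SAP 3.3.1.2 and Table 1, for the SSO tables only:
1. Assign Visit 3 laboratory, urinalysis, vital-sign and ECG assessments made before the IRT randomisation time to the inpatient period. The SAP already takes that date and time from the IRT. Where no assessment time is recorded, state a default, as SAP 3.3.1.1 does for first-dose-day assessments. Protocol 8.1.1 places vital signs and ECG before the potassium sample, and Protocol 8.2.4 has the local potassium result reviewed before randomisation, so a pre-randomisation default would be reasonable for vital signs and ECG.
2. Map the discharge or early-discontinuation assessment of non-randomised participants to the same end-of-inpatient visit.
3. Add an inpatient window for local potassium from after the first dose up to Visit 3.
4. Base the SSO QTcF categories and urinalysis shift on values after the first study dose.
5. Align Protocol Table 8, or record the departure in SAP section 2.

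Leave the adverse-event period rule unchanged. Cutting on randomisation time is cleaner than making the whole date inclusive, which could admit assessments made after randomisation that day.

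The cost is SAP wording, one extra analysis visit and the potassium window in the SSO programs, and a footnote explaining that Visit 3 appears in both SSO and SSR tables. No new data are required, and no dose or clinical rule changes.

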## **Outpatient Period**

The outpatient period refers to the period from the date of randomisation until the earliest date of end of treatment, withdrawal of consent, last contact with the participant or death (inclusive).

### **3.3.1.3 Handling of missing dates**

Incomplete dates (partial or missing dates where a full date is permissible) will be presented in the data listings as recorded on the eCRF. Missing hospital admission, emergency department and death dates will not be imputed. Every effort will be made to ensure complete information for these dates are available. However, for adverse event start and stop date and for prior and concomitant medication start and stop date, missing dates will be estimated as follows:

#### **3.3.1.3.1 Partial start dates**

If the year is unknown, then:

- The date will not be imputed, and will be assigned a missing value

If the month is unknown, then:

- If the year matches the year of the first dose date in the inpatient period, then impute the month and day of the first dose date.
- Otherwise, assign the month as July

If the day is unknown, then:

- If the month and year match the month and year of the first dose date in the inpatient period, then impute the day of the first dose date.
- Otherwise, assign the day as mid-month (14th for February, 15th for all other months).

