#### **3.3.1.3.2 Partial end dates**

If the year is unknown, then the date will not be imputed and will be assigned a missing value.

If the month is unknown, then assign July.

If the day is unknown, then assign the day as mid-month (14th for February, 15th for all other months).

If the above rules for end dates result in illogical date (i.e. end date < start date or end date > participant's date of completion/discontinuation) with regards to the dates the participant was in the study, then the end date will be replaced with the participant's date of completion/discontinuation.

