#### **3.3.1.4.2 Handling of Missing Safety Data**

In general, missing clinical laboratory data, vital signs and ECG data will not be imputed. Adverse event imputations for missing intensity or relationship are given in section 4.6.2.1. Unknown or partial medication and AE date imputations are given in section 3.3.1.3 and are to be used only for the assessment of prior / concomitant status for medications and treatment-emergent status for AEs.

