## **4.6.2      Adverse Events**

### **4.6.2.1    Definitions and Derivations**

All Adverse events, (non-serious and serious adverse events (SAEs) will be collected from time of signature of the informed consent form, throughout the treatment period including during the follow-up period. A treatment emergent AE (TEAE) will be defined as an AE with the start date on or after the first dose date during the inpatient period up to (and including) 7 days after the last dose date, and events with start date prior to the date of first dose of study treatment whose severity worsens on or after the date of first dose during the inpatient period.

TEAEs will be further categorised as either (i) occurring during the inpatient period, if the start date is on or after the first dose date during the inpatient period and prior to the date of randomization, (ii) occurring during the outpatient period if the start date is on or after the date of randomization and prior to the date of study treatment discontinuation+7.

MedDRA [Version 24.1 (or a later version if updated during the study)] will be used to classify AEs system organ class (SOC) and preferred term (PT).

Every effort should be made to collect the maximum intensity and relationship to treatment for all AEs. However, if the maximum intensity is missing for a TEAE then it will be considered as severe only in the overall category in the summary tables. If the relationship to treatment is missing, then the AE will be considered as possibly related to treatment.

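### The partial-date rules in SAP 3.3.1.3 can drop some on-treatment AEs from the summaries and turn some prior drugs into outpatient-concomitant ones

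*SAP*

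**What the plan says.** **Start dates (SAP 3.3.1.3.1).** Unknown month: "If the year matches the year of the first dose date in the inpatient period, then impute the month and day", both taken from the first inpatient dose. For any other year: "Otherwise, assign the month as July". Unknown day: "If the month and year match the month and year of the first dose date in the inpatient period, then impute the day of the", that is, the day on which SZC was first given in hospital. In other months: "Otherwise, assign the day as mid-month", which is the 15th, or the 14th in February. No logic check follows.

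**End dates (SAP 3.3.1.3.2).** "If the month is unknown, then assign July", and an unknown day becomes mid-month. A check does follow here. If the result is before the start, or after completion or discontinuation, it is illogical "with regards to the dates the participant was in the study, then the end date will be replaced with the" completion or discontinuation date.

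**Use.** SAP 3.3.1.4.2 says the imputed dates are "used only for the assessment of prior / concomitant status for medications and treatment-emergent status for AEs". SAP 4.6.2.1 runs the treatment-emergent window from the first inpatient dose "up to (and including) 7 days after the last dose date". SAP 4.6.2.2 lists AEs after that window but keeps them out of the summaries. SAP 4.1.8.1 calls a drug prior only if it stopped before the first inpatient dose. Listings show dates as recorded on the eCRF (SAP 3.3.1.3).

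**The concern.** The imputed date is the only thing that places such a record in or out of a table, so an implausible imputation becomes a classification error.

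For AE starts, mid-year is a poor guess in a study that follows each person for about half a year. If treatment runs into a second calendar year, it has nearly always ended before July. Nothing stops the imputed start from falling after study completion, or after the AE's own recorded stop date. The error removes events from safety summaries, which is the non-conservative direction.

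For medication stops, the check that should repair an impossible date replaces it with one that contradicts the recorded month or year. A drug known to have ended before first dose can then appear as outpatient use in the SZC versus SoC medication table.

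**Working it through.** The plan states no figure to reproduce, so the rules were applied literally.

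**Inputs**
- Stay from first dose to randomisation: 1, 7 or 20 days (SAP Table 3 puts Visit 3 on study day 2 to 21).
- Last SZC dose: 174, 180 or 186 days after randomisation (Visit 10 protocol window, SAP Table 3).
- Window end: last dose + 7 (SAP 4.6.2.1).
- Assumed: Arm A dosing to Visit 10; every first-dose date in 2022 and in 2023 equally likely; true AE dates uniform over the window.

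**1. AE start, month unknown, year after first dose**

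One case: first dose 2 Oct 2023, randomised 9 Oct 2023 (+7), last dose 6 Apr 2024 (+180), window end 13 Apr 2024 (+7). An AE dated '2024' is imputed to 15 Jul 2024 and falls outside, although every on-treatment day of 2024 is inside. An AE dated '2023' goes to 2 Oct 2023 and is kept.

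In general, let L = stay + days to last dose + 7. 15 July is day 196 of a non-leap year, so it is inside the window only for the last L − 196 + 1 first-dose dates of the year, or none if L < 196. For first doses in 2022:

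| Stay | Last dose | L | First-dose dates with window crossing year-end | Of these, 15 July inside | Next-year AEs lost | Share of all year-only treatment-emergent AEs lost |
|---|---|---|---|---|---|---|
| 1 | 174 | 182 | 182 | 0 | 100% | 24.9% |
| 7 | 180 | 194 | 194 | 0 | 100% | 26.6% |
| 7 | 186 | 200 | 200 | 5 | 95.1% | 26.0% |
| 20 | 180 | 207 | 207 | 12 | 88.8% | 25.2% |
| 20 | 186 | 213 | 213 | 18 | 83.8% | 24.5% |

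Row 2 by hand: next-year window days = 194 × 195 / 2 = 18,915; all window days = 365 × 195 = 71,175; 18,915 / 71,175 = 26.6%, all lost.

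Last row: next-year days = 213 × 214 / 2 = 22,791. The 18 saved dates (14 to 31 December) hold 196 + … + 213 = 3,681 of them. Lost: 19,110, which is 19,110 / 22,791 = 83.8% of next-year days and 19,110 / (365 × 214) = 24.5% of all window days.

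First doses in 2023 give nearly the same results (2024 is a leap year, so at most 17 dates are saved). When the month is known and only the day is missing, 1.6% to 1.7% are lost.

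**2. AE start known only to the first-dose month (minor)**

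In a month of D days with a 7-day stay, on-study days number D(D+1)/2, and those from randomisation on number (D−7)(D−6)/2. For D = 30 that is 276 / 465 = 59%; for D = 31, 300 / 496 = 60%. All such AEs are dated at the first inpatient dose. Under SAP 4.6.2.2 they enter the single-group SSO inpatient table. They also stay in the SSR table by arm, which includes all AEs.

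**3. Medication stop imputed before the start**

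Same participant, completion 13 Apr 2024:
- Start 20 Sep 2023, stop 'Sep 2023': imputed 15 Sep, before the start, so replaced by 13 Apr 2024. The drug certainly stopped before 2 Oct, yet moves from prior to outpatient-concomitant.
- Start 1 Sep 2023, stop '2023': imputed 15 Jul 2023, before the start, so replaced by 13 Apr 2024, a date outside the recorded year.
- Start 2020, stop '2023': imputed 15 Jul 2023, not before the start, so classed as prior.

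**The case against.** The strongest reply is that the trigger should be rare. AEs are asked about at every visit (Protocol 1.3), a start date is collected for each (Protocol 8.3.2), SAEs go to the sponsor within 24 hours (Protocol 8.3.6), and data are cleaned before lock (SAP 3.1). This stands as a limit on size. The documents give no count of partial dates, so the overall effect cannot be estimated. The percentages above are conditional on a partial date of the stated kind.

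Four stronger readings are tempting, and the documents do not support them.
- *The AE and medication tables are wrong.* Complete dates are untouched, same-year AE starts go to first dose and are counted, and many partial stops classify correctly.
- *Post-discharge AEs are moved out of the randomised comparison.* They are not: the SSR summaries include AEs from both phases. At most, such an AE is also counted in the SSO table.
- *About half of same-month stops are misclassified.* 186 of 365 calendar dates (51%) fall after the imputed mid-month day, but that is not an error rate. A drug started after randomisation is outpatient-concomitant whatever its stop date. If all start/stop pairs within a month are equally likely, only 1,537 of 5,738 (27%) start after mid-month.
- *Efficacy is affected.* SAP 3.3.1.4.2 confines the imputed dates to status, and admission, ED and death dates are not imputed (SAP 3.3.1.3).

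It can also be said that over-including medications matches the SAP's own default, since SAP 4.1.8.1 sends unclassifiable drugs to outpatient-concomitant. That default covers drugs that cannot be classified. A drug whose recorded stop month ended before first dose can be.

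Finally, the AE figures describe Arm A. Arm B leaves hospital without SZC (Protocol 6.2), so a window tied to the last dose closes soon after discharge even for exact dates. That is a separate matter, not caused by the July rule.

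**Conclusion.** The point holds as a defect in the written rules, limited to records with partial dates. In Arm A, under the dosing and uniform-date assumptions above, 84% to 100% of true treatment-emergent AEs with a year-only start in the year after first dose leave the summaries. The other 73% to 75% of year-only treatment-emergent AEs are kept. The medication defect is narrower. It needs an imputed stop before the start and a drug that truly stopped before the outpatient phase, and its error is over-inclusion. The first-dose-month rule is minor. The AE summaries and medication tables concerned are descriptive, and the listings still show the recorded dates. The AE rule is nevertheless worth correcting because it errs against safety reporting and the repair is simple.

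**What to change.** **Start dates.** If the month is unknown and the year is later than the first-dose year, impute 1 January of that year, the earliest date consistent with what is known. Every window that crosses the year-end contains 1 January, so the loss in step 1 falls to 0%. Never impute a start later than the record's own end date or the last contact.

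**End dates.** Leave the July and mid-month rules as they are. Only when the imputed stop falls before the start, use the last day of the known month (or year), capped at death or completion, in place of the completion date. Keep a drug as prior when its known stop month or year ended before first dose. The 20 September drug then ends on 30 Sep 2023 and stays prior.

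Do not move every year-only stop to year-end. A drug started in 2020 and stopped in '2023', which the current rule can correctly class as prior to an October 2023 first dose, would become concomitant.

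The cost is a few sentences in SAP 3.3.1.3 and a few lines of derivation code. The downside is that slightly more AEs will count as treatment-emergent.
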